9.7 Pregnancy reporting

Pregnancy is not considered an AE unless a negative or consequential outcome is recorded for the mother or child/foetus. If the outcome meets the serious criteria, this would be considered an SAE.

10 STATISTICS AND DATA ANALYSIS

10.1 Sample size calculation

The sample size required for Stage 1 is based on an assumed prevalence of insomnia of 44% in breast cancer patients (midway point of insomnia prevalence range found in breast cancer patients 19-69%)⁴⁻¹⁰. A sample size of 267 participants is required for estimating the expected prevalence rate with 5% absolute precision and 90% confidence or 6% absolute precision and 95% confidence²⁹.

The target for Stage 2 is for approximately 100 participants to complete the study, to provide sufficient data to assess the secondary objectives. With an assumed prevalence of 44% and a 20% drop out rate, then 285 participants in Stage 1 would give an expected 125 eligible participants for Stage 2 with 100 participants assumed to complete the 3-week observation period.

Therefore, the study will aim to recruit a minimum of 285 patients into Stage 1 to cover the sample size requirements for Stage 1 and Stage 2.

10.2 Planned recruitment rate

Recruitment will take place over a four-month period and is planned to end (last participant enrolled) by January 2022. Expected recruitment rate for Stage 1 is aimed at 15 participants per week with approximately half of these (7-8 participants per week) being eligible for Stage 2 of the study.

10.3 Statistical analysis plan

The analyses will be carried out according to the statistical analysis plan (SAP) which will be prepared prior to database lock. The SAP will describe the statistical methods to be used in the analysis and reporting of study data.

10.3.1 Summary of baseline data

Baseline demographic data will be summarised for all participants enrolled in Stage 1, and separately for those in Stage 2. In general, continuous variables will be summarised using the following standard descriptive summary statistics: number of observations, mean, standard deviation (SD), median, minimum, and maximum. Categorical data will be summarised as the number and percentage of participants in each category.

10.3.2 Primary outcome analysis

The prevalence estimates for insomnia in the breast cancer cohort studied will be reported as the number and percentage of screened patients in Stage 1 determined as having insomnia by the ISI (total score of 8 or more) and accompanied with exact 95% confidence intervals. Prevalence rates and 95% confidence intervals will also be reported by breast cancer stage (Stages I, II and III) and type of breast cancer treatment.

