Secondary Objectives	
 1. In patients with breast cancer experiencing insomnia (defined as score of 8 or more on the Insomnia Severity Index; ISI scale), to assess the following parameters over a three-week period 
 i) Insomnia Severity ii) Sleep efficiency iii) Quality of Life 2. To assess, at the end of the three-week assessment period, 
 i) Compliance of data entry into the digital sleep diary ii) Feasibility and experience of patients with breast cancer to input data relating to their sleep into a mobile phone application daily iii) Safety related to using the digital sleep diary 3. To determine associations between insomnia prevalence and severity and quality of life with clinical or treatment characteristics of breast cancer patients.
Primary Outcome Measures	
Prevalence of insomnia defined as the proportion of screened patients determined as having insomnia defined as a score of 8 or more on the ISI.
 
Prevalence of insomnia will be determined by administration of the Insomnia Severity Index questionnaire to participants in Stage 1 of the study. Participants scoring 8 or above will be categorised as having insomnia.

Secondary Outcome Measures	
 1. In patients with breast cancer experiencing insomnia (defined as score of 8 or more on the Insomnia Severity Index; ISI scale), to assess the following parameters over a three-week period 
 i) Proportion of patients in each Insomnia Severity category measured using the ISI ii) Sleep efficiency calculated from sleep diary entries iii) Quality of Life index values obtained from EQ-5D-5L and Functional Assessment of Cancer Therapy - Endocrine Symptoms (FACT-ES). iv) Compliance of data entry into the digital sleep diary v) User experience and feasibility of the digital sleep diary assessed using the User Experience Questionnaire (UEQ) vi) Safety assessed by Adverse events (AEs), particularly AEs considered associated with the digital sleep diary. 2. Insomnia prevalence and severity and quality of life assessed by clinical or treatment characteristics of breast cancer patients.

IV. FUNDING AND SUPPORT IN KIND**FUNDER(S)**

(Names and contact details of ALL organizations providing funding and/or support in kind for this trial)

Closed Loop Medicine Ltd.
[name]
Babraham
Cambridge
[name]
Email: [contact]

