3.3 Primary endpoint/outcome

Primary evaluation criteria:

- i. Prevalence of insomnia in the screened cohort of patients with breast cancer; including subsidiary breakdown by breast cancer stage and type of breast cancer treatment. Prevalence of insomnia will be assessed as the proportion of screened patients determined as having insomnia according to the ISI total score (where a score of 8 or more indicates insomnia).

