6 PARTICIPANT ELIGIBILITY CRITERIA

6.1 Inclusion criteria

To be eligible to participate in Stage 1, the following criteria must be met:

1. Age ≥ 18 years.
2. Informed consent to Stage 1 of the study.
3. Diagnosis of Stage I, II or III Breast Cancer within the previous 12 months.

To be eligible for Stage 2 of the study, the following criteria must be met:

1. Informed consent to Stage 2 of the study.
2. Current Sleep Disturbance; a score of 8 or more on the Insomnia Severity Index.
 - Total ISI score categories: 0–7 = No clinically significant insomnia
8–14 = Subthreshold insomnia
15–21 = Clinical insomnia (moderate severity)
22–28 = Clinical insomnia (severe)
3. History of sleep disturbance prior to the screening/baseline consultation; with beginning or worsening of sleep disturbance since breast cancer diagnosis e.g. sleep problems began or get worse with the diagnosis of breast cancer or with chemotherapy.
4. Possession of a suitable smartphone that participant can use independently.

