7.3.1 Stage 1 Electronic Consent (eConsent)

Participants will be contacted by the clinical study team by text message. This text message will give some brief information about the study and an internet link to the study information including the Patient Information Sheet (PIS) and Informed Consent Form (ICF). If required, initial contact can also occur by email, telephone and/or online video conferencing. In these instances, the potentially eligible participant will be provided with the same internet link as above. Moreover, the initial contact can also be face to face in the clinic. The PIS and ICF to be used in the study will be approved by the Research Ethics Committee (REC) and follow GCP guidelines. These documents have been designed to be viewed and completed by patients on their smartphone. If required, these documents can also be accessed by a computer or tablet. Patients will be given time to consider taking part in the study and provided with contact details of the clinical study team to discuss any questions they may have regarding the study. If willing to participate, they will be asked to complete the ICF. At this stage the participant will be asked to provide their email address and mobile phone number for the purposes of sending study questionnaires and further study information. If no response has been received from potential participants within 3 days of the receiving the first text message, the initial text message will be sent again.

A proportionate approach to eConsent in guidance with the MHRA/HRA Joint Statement regarding seeking consent using electronic methods will be taken²². The HRA indicate that it is not necessary to include a PIS or ICF for online questionnaire-based research²³. However, we have taken the decision to provide patients with these documents to ensure they have sufficient information to enable them to reach an informed decision to take part. As the study is observational and low risk, participants will confirm participation in the trial by simple e-signature on the ICF. Within the ICF, participants will be asked to consent to the use of their personal data for the purposes of sending online questionnaires and for the Sponsor to have access to this data for monitoring purposes. Participants will also be asked to consent to being contacted to take part in Stage 2 of the study. See Figure 1 for an outline of the eConsent process.

[figure not shown]

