7.4.1 Stage 2 Eligibility Assessment

All questionnaire-derived eligibility-related data for each participant will be present within the eCRF. This will enable the clinical study team to populate the eligibility eCRF including ISI scores and data related to self-reported sleep history, sleep apnoea, shift-work or night-work, possession of smartphone and breast feeding. The EDC will be configured to automatically calculate the total ISI score required for assessment of eligibility to Stage 2. The clinical research team will be required to confirm from patient medical records the stage of breast cancer, any other diagnosis of cancer, not including basal cell carcinoma of the skin or cervical carcinoma in situ, within the previous 5 years, and any comorbidities incompatible with study participation.

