7.4.4 Clinical Data Capture

Upon receiving and reviewing completed Stage 2-specific ICF, the study team will review patient medical records and capture required data for the following eCRFs:

Cancer Medical History: capturing data regarding, time since cancer diagnosis, cancer stage, primary or secondary cancer, surgery type, neoadjuvant or adjuvant treatment, and positivity for oestrogen receptors (ER), progesterone receptors (PR) or human epidermal growth factor receptor 2 (HER2).

Cancer Treatment: current breast cancer treatment broken down by chemotherapy, radiotherapy, and hormonal therapy and information regarding current medication cycle.

Current Co-morbidities: current co-morbidities and whether each co-morbidity is being treated with medication.

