### 2.2. Definitions of Analysis Sets

The following analysis sets will be used in the statistical analyses and reporting of study data.

- Stage 1 analysis set will include all participants who consented to stage 1, are eligible for the study and have evaluable data for at least one of the questionnaires (ISI, EQ-5D-5L or FACT-ES).
- Stage 2 analysis set will be a subset of the Stage 1 analysis set and will include eligible Stage 1 participants who scored  $\geq 8$  on their baseline ISI questionnaire and consented to stage 2. Note if a patient consents to Stage 2 but does not provide **any** stage 2 data (e.g., questionnaire/sleep data) then they will be excluded from the stage 2 analysis set.

Statistical Analysis Plan for CLM-INS-004

Version: Final 2.0

Date: 9th September 2022

Note, listings will generally be based on the stage 1 analysis set with an indicator for patients who also entered into stage 2, with the exception of the cancer history, cancer treatment, co-morbidities, sleep diary, AE and UEQ listings which will be based on the stage 2 analysis set since these are only completed for stage 2 patients.

If a participant does not enroll in the digital diary (i.e., does not even download the app) but completes the UEQ, then data from the UEQ will not be included in the reporting of the data.

Percentages will generally be derived based on the analysis set N as the denominator, unless stated otherwise. Where there is missing data, % may be derived based on those within the analysis set who have evaluable data. Where applicable missing categories will be included to show the number of patients with missing data for the relevant endpoint.

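### Insomnia prevalence by cancer stage and treatment cannot be produced from the planned data, because both are entered only for Stage 2 participants, all of whom have ISI ≥8

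*Protocol*

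**What the plan says.** **The promise.** Protocol 3.3 defines the primary endpoint as prevalence in the screened cohort, "including subsidiary breakdown by breast cancer stage and type of breast cancer treatment". Protocol 10.3.2 repeats this as part of the primary analysis: "Prevalence rates and 95% confidence intervals will also be reported by breast cancer stage (Stages I, II and III"), and by treatment type. The study summary adds a secondary outcome: "Insomnia prevalence and severity and quality of life assessed by clinical or treatment characteristics of breast cancer patients". Protocol 3.4 (viii), 3.5 and 10.3.3 and SAP 1.1 say the same in substance.

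**The data.** Table 1 and Protocol 7.3.3 limit Stage 1 to the ISI, EQ-5D-5L, FACT-ES, demographics and sleep history. Cancer history and treatment come later (Protocol 7.4.4): "Upon receiving and reviewing completed Stage 2-specific ICF, the study team will review patient medical records and capture required data for the following eCRFs". SAP 2.2 confirms this for the listings of cancer history and treatment, "which will be based on the stage 2 analysis set since these are only completed for stage 2 patients". SAP 3 summarises these data for the Stage 2 set only.

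**The gate into Stage 2.** Protocol 6.1 requires "Current Sleep Disturbance; a score of 8 or more on the Insomnia Severity Index".

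**The planned outputs.** SAP 3.2.1 gives overall prevalence only. SAP 3.6 covers severity, sleep efficiency and quality of life in the Stage 2 set, without prevalence. SAP 4 lists four changes from the protocol, and the loss of the prevalence breakdown is not named among them.

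**The concern.** Prevalence in a stratum needs both cases and non-cases of that stratum in the denominator. Here the stratifying variables are recorded only for people who have already met the case definition. The breakdown attached to the primary endpoint, and the prevalence part of the association outcome, therefore cannot be computed from the planned dataset.

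The plan also contradicts itself. SAP 1.1 tells the reader to expect subgroup prevalence, the SAP's analysis sections do not provide it, and its list of changes does not mention it. Protocol 10.5 requires changes to the analysis plan to be recorded in the SAP with a reason.

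A secondary consequence concerns SAP 3.6. Its summaries describe only Stage 2 participants with ISI ≥8, whereas the association objective (Protocol 3.2, item 3) is worded for breast cancer patients generally. Selecting on the outcome may attenuate severity differences between groups, but the documents do not establish the size or net direction of that effect.

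**Working it through.** **1. The plan's own figures reproduce.** Inputs from Protocol 10.1: prevalence p = 0.44; 267 needed; 285 recruited; 125 eligible for Stage 2; 20% drop-out; 100 completing. With n = z²p(1−p)/d²:

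- 90% confidence, d = 0.05: 1.645² × 0.44 × 0.56 / 0.05² = 266.7, so 267, as stated.
- 95% confidence, d = 0.06: 1.960² × 0.44 × 0.56 / 0.06² = 262.9, so 263, which 267 covers.
- Stage 2: 285 × 0.44 = 125.4, and 125 × 0.8 = 100, as stated.

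**2. Who has stage and treatment recorded.**

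| Stage 1 participant | Cancer stage | Treatment |
|---|---|---|
| ISI below 8 | not captured | not captured |
| ISI ≥8, does not enter Stage 2 | confirmed from records if assessed (Protocol 7.4.1); storage not stated | not captured |
| ISI ≥8, enters Stage 2 | captured | captured |

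**3. How many lack the data.**

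- Non-cases at 44%: 285 × 0.56 = 159.6, about 160 (56%).
- Over the 19–69% range quoted in the protocol, with 285 recruited: 285 × 0.81 = 230.9 down to 285 × 0.31 = 88.4, about 231 to 88.
- For treatment, add people with ISI ≥8 who do not enter Stage 2. The documents give no entry rate, so 80% and 60% are assumptions: 285 − 125.4 × 0.8 = 184.7 (65%), and 285 − 125.4 × 0.6 = 209.8 (74%).

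**4. Why the Stage 2 set cannot stand in.** Every member is a case, so each stratum gives n/n = 100% whatever the true prevalence. If all 125 entered and split into equal thirds (assumption), each cancer stage would show 42/42, exact 95% CI 91.6–100%.

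**5. What full capture would give.** The documents give no stage or treatment distribution, so the stratum sizes below are assumptions. Clopper-Pearson 95% intervals at about 44%:

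| Group | Cases/n | 95% CI | Half-width (points) |
|---|---|---|---|
| All Stage 1 | 125/285 | 38.0–49.8% | 5.9 |
| Equal thirds | 42/95 | 34.0–54.8% | 10.4 |
| Smaller stratum | 22/50 | 30.0–58.7% | 14.4 |
| Small stratum | 13/30 | 25.5–62.6% | 18.6 |

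**The case against.** The strongest reply is that the information exists at the site. Stage I–III disease is a Stage 1 inclusion criterion (Protocol 6.1), records are read before invitation (7.2), and 11.2 has site staff transcribing baseline data from records into the eCRF without limiting this to Stage 2. At the Stage 2 eligibility step, "The clinical research team will be required to confirm from patient medical records the stage of breast cancer". This shows that the gap can be repaired, more easily for cancer stage than for treatment. It does not show that the data are planned: no Stage 1 eCRF field for either variable is described, and only those scoring ≥8 are assessed for Stage 2.

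Second, the SAP is open about restricting cancer data to Stage 2, and SAP 4 lists a clarification of analysis sets. That is fair, so the restriction itself is not hidden. But the entry does not say that a protocol analysis has been lost.

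Third, nobody proposes to estimate prevalence in the Stage 2 set. That is true. The 100% figure only shows why the one set with the stratifiers cannot substitute.

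Fourth, the breakdown is subsidiary and descriptive, and SAP 1.2.1 allows fewer recruits if prevalence is higher, so the count of 88 at the upper end holds only if 285 are recruited. Both points stand. They limit the weight and precision of the finding, not its substance. It is also reasonable for SAP 3.6 to report sleep efficiency and Day 21 outcomes in Stage 2, because those are collected only there.

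**Conclusion.** The concern holds. Prevalence by cancer stage and treatment is promised in the primary endpoint, the primary analysis and a secondary outcome, and it cannot be delivered from the data as planned. About 160 of 285 participants (56%) would have neither variable at 44% prevalence. For treatment the figure is about 185 to 210 if 80% to 60% of those with ISI ≥8 enter Stage 2. The counts rest on the protocol's assumed prevalence and on 285 recruits; the entry rates and stratum sizes are assumptions.

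The conclusion itself does not depend on them, because it follows from the entry criterion and the timing of data capture. Overall prevalence and its interval are not affected. This should be fixed, but it does not threaten the main result.

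**What to change.** **Preferred.** For every Stage 1 participant not in Stage 2 (non-cases, plus those with ISI ≥8 who are ineligible or decline), abstract cancer stage and treatment type from medical records, as at the date of the Stage 1 ISI and using the existing Stage 2 eCRF categories. Add to the SAP prevalence with exact 95% CIs by stage and by treatment on the Stage 1 set, labelled descriptive and of limited precision. Baseline severity and quality of life by the same characteristics on that set would be a useful option, but the repair does not depend on it.

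*Cost:* two or three fields for about 160 non-cases, or about 185–210 people in all under the entry rates assumed above, with no extra patients or visits. Consent must be checked first. The form was not among the documents reviewed, and the uses described in Protocol 7.3.1 are narrow: "Within the ICF, participants will be asked to consent to the use of their personal data for the purposes of sending online questionnaires", Sponsor access for monitoring, and contact about Stage 2. Recruitment was due to end by January 2022 and the SAP is dated September 2022, so an ethics amendment or re-consent may be needed.

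**Fallback, if capture is not possible or not permitted.** Delete the prevalence breakdown from the study summary, Protocol 3.3, 3.4 (viii), 3.5, 10.3.2 and 10.3.3, and SAP 1.1. List the deletion and its reason in SAP 4, and state in SAP 3.6 that its summaries apply only to Stage 2 participants with ISI ≥8.

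*Cost:* wording only, in those seven places plus SAP 3.6 and 4.

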10.3.3 Secondary outcome analysis

Insomnia severity will be assessed by calculating proportions (number and percentage) of participants within each of the ISI categories:

- no clinically significant insomnia (ISI score 0-7)
- subthreshold insomnia, (ISI score 8-14)
- clinical insomnia of moderate severity (ISI score 15-21)
- severe clinical insomnia (ISI score 22-28).

Percentage of participants in each severity category at baseline/screening will be derived and summarised based on all screened patients from data obtained during stage 1 (baseline/screening assessment). In addition, percentage of patient in each severity category will also be assessed only in those patients determined to have insomnia (i.e. enrolled patient in Stage 2) at both screening/baseline and day 21.

To determine sleep efficiency, the % of time a participant is asleep whilst in bed will be derived based on total time asleep relative to total time in bed. Sleep efficiency will be derived and assessed over the last 2 weeks of the 3-week observation period to correspond with the insomnia severity assessment which is also based on the last 2 weeks. Other timepoints may also be assessed (e.g. weekly).

Quality of Life Data from the EQ-5D-5L self-classifier, which includes five dimensions (mobility, self-care, daily activities, pain/discomfort, and anxiety/depression), will be used to calculate an index value as a measure of the participant's health, both at screening/baseline (all screened patients; Stage 1) and following the observational period (all enrolled patients; Stage 2). Data will be summarised descriptively.

Quality of Life Data from the FACT-ES self-report measure, which includes five subscale domains (physical well-being, social/family well-being, emotional well-being, functional well-being, and endocrine symptom subscale), will be used to calculate an index value as a measure of the participant's health, both at screening/baseline (all screened patients; Stage 1) and following the observational period (all enrolled patients; Stage 2). Data will be summarised descriptively.

Compliance of entry into the digital sleep diary will be assessed as the proportion of participants completing the digital sleep diary on at least 17 out of 21 days and summarised descriptively.

Reporting of user experience data collected from the UEQ at Day 21 will be descriptive.

All Reported AEs and SAEs will be coded according to the latest version of the Medical Dictionary for Regulatory Activities (MedDRA) and presented by SOC and PT. In addition, any AEs/SAE considered related to the usage of the sleep diary will be summarised separately (or listed if numbers are low).

To assess any association with treatment/clinical characteristics and insomnia prevalence, insomnia severity, sleep efficiency and Quality of Life, data will be reported and summarised by breast cancer stage, treatment regimen and baseline insomnia severity. Other clinical or treatment groups may also be explored. Full details of the characteristics to be assessed will be provided in the SAP.

